Haemolysis	Widespread erythrocyte cell membrane destruction	Haemoglobin measured daily. Treating clinician requests haemolysis screen if indicated. -	- Laboratory evidence of haemolysis (e.g., direct antiglobulin test; schistocytes; decreased haptoglobin) AND - Loss of > 2 g haemoglobin within 24 hours (2 blood tests closest to 24 h apart) AND - Transfusion or medical intervention (i.e. steroids) indicated AND - No other potential cause than the intervention	Evidence of haemolysis within 24 hours of Omegaven infusion Transfusions that occur within 24 hours of diagnosis of haemolysis	- Document and contact CI
Hyper-triglyceridaemia	Elevated levels of triglycerides in blood	- Measured daily	- Triglycerides > 530.97 mg/dl (6 mmol/l) ³⁰	If occurs at any point during the infusion or within five half-lives (5 hours) of finishing the infusion	Stop infusion Document and contact CI
Reticulocytosis	Increase in circulating reticulocytes (immature red blood cells) as sign of accelerated erythrocyte production	- Measured daily.	Reticulocytes >100 x10 ⁹ /I ³⁴ AND No other potential cause than the intervention AND Need for transfusion within 24 hours of diagnosis	- Need for transfusion within 24 hours of diagnosis	- Document and contact CI
Thrombocytopenia	Deficiency of blood platelets	- Measured daily.	 Platelets <50 x10⁹ with requirement of platelet transfusion AND 	Within 24 hours of infusionTransfusions that occur within 24 hours	- Document and contact CI

HIPPO V3.0 14/02/2025 Page 19 of 62

			Absence of other causes of thrombocytopenia such as therapeutic agents (e.g. heparin), chronic diseases	of diagnosis of thrombocytopenia	
Thrombophlebitis	Inflammation in the vein in the presence of an intravenous catheter	 Identified on clinical examination by staff or by patient if conscious. Absence of documentation will be considered to indicate no concern. 	 Grade 3 (Pain at the puncture site with erythema, hardening and a palpable venous cord) OR Grade 4 (Pain at the puncture site with erythema, hardening and a palpable venous cord that is > 1 cm, with purulent discharge) 	If occurs within 24 hours of any Omegaven infusion, specific to the cannula used to infuse Omegaven.	- Document and contact CI

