4.0 Informed consent procedures

Informed consent will be obtained prior to the participant undergoing trial specific procedures at a participating site. All consent procedures will be documented in detail in the patient's medical notes. The consent procedure is the same for patient's randomise to the standard of care arm or the intervention arm.

Patients admitted to critical care are frequently unable to consent for themselves due to severity of illness, neurological impairment, sedation, delirium, trauma, etc. Similarly, having a relative in an emergency clinical situation often causes profound distress for the next of kin of the patient. It would be unethical and inappropriate to add to this stressful and emotional situation by asking them to make a decision on trial enrolment on behalf of the patient. Therefore, in cases where a patient is unable to provide consent, HIPPO will adopt a "research with delayed patient consent" model, where eligible patients will be enrolled initially through written informed consent from a Professional Legal Representative (independent clinician with clinical responsibility for patient care not involved in the trial). After professional consent is received, and the patient still does not have the capacity to consent, then a Personal Legal Representative (a family member, partner or close friend) will be approached. This is an

accepted model of consent in adult emergency and critical care research where participants are likely to lack capacity to consent and where the distress and burden on the Personal Representative should be minimised.³⁷ This model is used in a variety of other studies recruiting patients from the Adult Critical Care Unit. ³⁷⁻³⁹

The Principal Investigator (PI) has overall responsibility for the informed consent of participants at their site and will ensure that any person delegated responsibility to participate in the informed consent process is duly authorised, trained, and competent to participate according to the ethically approved protocol, principles of Good Clinical Practice (GCP), and Declaration of Helsinki. If delegation of consent occurs, then details will be provided in the site delegation log. Delegation can only be to members of the research team (which include research nurses, doctors).

Immediate patient informed consent:

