6.0 Participant eligibility criteria

6.1 Inclusion criteria

- Age 18 years and over
- Patients requiring intubation and ventilation OR two or more other organ systems support (Sequential Organ Failure Assessment (SOFA) score ≥2 in >2 domains) without requiring intubation and ventilation.⁴⁰
- Patients predicted to remain in critical care for at least 72 hours as determined by the
 Intensive Care Consultant with clinical responsibility for patient care.

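### Both countable thrombophlebitis grades in Table 1 require pain at the puncture site, with no rule for patients who cannot report it, so this DLT may be under-counted

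*Protocol*

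**What the plan says.** In section 2.6, Table 1, the thrombophlebitis row counts two grades:

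- "Grade 3 (Pain at the puncture site with erythema, hardening and a palpable venous cord"
- "Grade 4 (Pain at the puncture site with erythema, hardening and a palpable venous cord that is > 1 cm, with purulent discharge"

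The identification column of that row says "Identified on clinical examination by staff or by patient if conscious" and then "Absence of documentation will be considered to indicate no concern". The event must fall within 24 hours of an Omegaven infusion and concern the cannula used for it.

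Section 6.1 admits "Patients requiring intubation and ventilation OR two or more other organ systems support". Section 4.0 describes critical care patients as "frequently unable to consent for themselves due to severity of illness, neurological impairment, sedation, delirium, trauma". Sections 7.0 and 11.9 make central access the first choice and peripheral access the fallback.

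A Table 1 event that the panel judges definitely or probably related to Omegaven counts towards the DLT rate. Each patient counts once (section 2.6, note e to Table 3). With nine evaluable patients, Table 3 says escalate at 2 or fewer, stay at 3, and eliminate at 4 or more.

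The haemolysis row contains the condition "Loss of > 2 g haemoglobin within 24 hours", without a volume.

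**The concern.** The identification column was written with unconscious patients in mind; the criteria column was not. Pain is joined to the physical signs in both grades. Taken at its word, the row does not say how to classify an unconscious patient who has erythema, hardening, a long palpable cord and purulent discharge. Pain that nobody can report will tend not to be recorded, and the row turns missing documentation into no event. The panel adjudicates only after each dosing phase, so it is likely to depend on what was written down at the time.

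The sponsor added thrombophlebitis to the list on purpose. Table 1 events are what feeds the DLT rate, the dose decisions and the isotonic estimate of the maximum tolerable dose, which is the only primary outcome. An event dropped because of the patient's level of consciousness makes a dose look better tolerated than it was. This definition operates during the trial, so a later analysis plan cannot repair it.

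**Working it through.** **1. The texts side by side**

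| Element of the thrombophlebitis row | Works without a patient report? |
|---|---|
| Identification: staff examination, or the patient if conscious | Yes |
| Erythema, hardening, palpable cord, purulent discharge | Yes, observable |
| Pain, required in both grades | Not stated |
| Nothing documented | Treated as no event |

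The urticaria row has the same identification wording and describes an itchy rash. Its criteria, however, are body surface area and need for IV intervention, and neither depends on a symptom report. Table 1 therefore already contains a row that solves this problem.

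**2. The decision rule itself**

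Inputs from section 2.6: target φ = 0.30, cohorts of nine, overdose cut-off 0.80. Assumed, because the protocol does not state them: the usual BOIN defaults φ1 = 0.6φ = 0.18 and φ2 = 1.4φ = 0.42, and a Beta(1,1) prior for elimination.

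- Escalation boundary: ln[(1−φ1)/(1−φ)] / ln[φ(1−φ1)/(φ1(1−φ))] = ln(0.82/0.70) / ln(0.246/0.126) = 0.2365 (protocol: 0.236).
- De-escalation boundary: ln[(1−φ)/(1−φ2)] / ln[φ2(1−φ)/(φ(1−φ2))] = ln(0.70/0.58) / ln(0.294/0.174) = 0.3585 (protocol: 0.359).
- Elimination: the smallest count with P(p > 0.30) > 0.80 is 4 of 9. The whole elimination row of Table 3, for 3 to 27 patients, is reproduced.

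The rule is sound as stated. The issue is what is counted.

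**3. One missed patient among nine**

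| True count | Decision | Count with one missed | Decision | Changed? |
|---|---|---|---|---|
| 1 | escalate | 0 | escalate | no |
| 2 | escalate | 1 | escalate | no |
| 3 | stay | 2 | escalate | yes |
| 4 | eliminate | 3 | stay | yes |
| 5 | eliminate | 4 | eliminate | no |

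The change also requires that the missed patient has no other DLT. At the lowest dose, 4 read as 3 means continuing where the rule would stop the trial. At the highest dose, 3 read as 2 cannot escalate further, but it still lowers the rate that enters the isotonic estimate.

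**4. Illustration only**

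The documents give no event rates, so these are assumed: risk of another DLT a, risk of countable thrombophlebitis t, independent of each other, and share s of thrombophlebitis events not counted. The observed DLT rate is q = 1 − (1−a)(1 − t(1−s)). The count X is Binomial(9, q).

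| a | t | s | q | P(X ≤ 2), escalate | P(X ≥ 4), eliminate |
|---|---|---|---|---|---|
| 0.30 | 0.05 | 0 | 0.335 | 0.373 | 0.354 |
| 0.30 | 0.05 | 0.5 | 0.318 | 0.417 | 0.311 |
| 0.30 | 0.05 | 1 | 0.300 | 0.463 | 0.270 |
| 0.30 | 0.10 | 0 | 0.370 | 0.292 | 0.442 |
| 0.30 | 0.10 | 0.5 | 0.335 | 0.373 | 0.354 |
| 0.30 | 0.10 | 1 | 0.300 | 0.463 | 0.270 |

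With t = 0.10 and all such events missed, P(escalate) goes from 0.398 to 0.601 when a = 0.25, and from 0.205 to 0.337 when a = 0.35. The direction is the same throughout; the size depends entirely on the assumed inputs.

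**The case against.** A reader might infer that the DLT cannot be met in sedated patients, so that its sensitivity there is zero. The documents do not support that. The criterion says pain, not patient-reported pain, and staff examination is an accepted route, so an examiner might accept observed signs of pain. What stands is that the protocol does not say so and leaves the count to each reader.

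Several facts limit the number of events affected, and all of them stand:

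- Central access is first choice, and the event is tied to the Omegaven cannula.
- Section 6.1 also admits patients who are not ventilated. Section 4.0 concerns capacity to consent, which is not the same as ability to show pain, and it plans for capacity returning.
- A severe case could enter through the row for other events if the consultant is concerned and it reaches CTCAE Grade 3. This backstop is partial: it covers the infusion plus five hours, against 24 hours in the thrombophlebitis row.

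A reader might also take the missing haemoglobin unit as a tenfold ambiguity in a primary-outcome criterion (2 g/dl is 20 g/l, against 2 g/l). The row compares two blood tests, so a concentration is meant, and the per-litre reading is implausible. The drop is also joined by AND to laboratory evidence of haemolysis, an indicated transfusion or medical intervention, and the absence of any other potential cause. It is a drafting omission and not a finding in its own right.

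**Conclusion.** The point holds as a gap in an endpoint definition. Both countable grades need pain, the row gives no rule for patients who cannot report it, and the documentation default pushes towards not counting. The likely error is an under-count that favours escalation. Its size cannot be derived from the protocol, which gives no sedated share, peripheral-access share or thrombophlebitis rate. Under the assumed thrombophlebitis risks of 0.05 to 0.10 and another-DLT risk of 0.30, missing every such event would raise the chance of escalating after one cohort from between 0.29 and 0.37 to 0.46. That is an upper case for those inputs, not an estimate. A single missed patient matters at nine only when the true count is 3 or 4 and that patient has no other DLT. The gap is worth closing because it sits in the sole input to the primary outcome and is cheap to close.

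**What to change.** Reconcile the identification and criteria columns of the thrombophlebitis row, so that the DLT can be counted from staff-observed signs when the patient cannot report pain. One way is to let the objective signs already listed in each grade suffice in that case, with the sponsor confirming the grading. Match the CRF field, so that the panel can see which signs were present and whether the patient could report pain.

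The cost is one line in Table 1 and one CRF change; the BOIN boundaries and Table 3 are untouched. The downside is slightly lower specificity, with the panel's causality assessment still applying.

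As a clerical correction in the same table, print the volume unit for the haemoglobin loss, as the triglyceride and reticulocyte rows already do for theirs.

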2.6 Trial design

To improve transparency, completeness, reproducibility and trial usefulness of this early phase dose-finding trial, the Standard Protocol Items: Recommendations for Interventional Trials Dose-finding Extensions (SPIRIT-DEFINE) guideline ²⁵ has been followed. This is a dose-escalation, randomised controlled trial, where critically ill patients will receive either Omegaven or standard care for 10 days or until hospital discharge, whichever is sooner. The Bayesian Optimal Interval (BOIN) design is being used to specify the dose-escalation/ de-escalation decision strategy whereby the observed dose-limiting toxicity (DLT) at each dose level is

compared with a pair of escalation and de-escalation boundaries optimised to minimise the risk of patients receiving overly toxic or subtherapeutic doses.²⁶ The BOIN design implemented in HIPPO is similar to the traditional 3+3 design but provides more flexibility and possesses superior operating characteristics that are comparable to those of more complex model-based designs.²⁷

Dose-limiting toxicity assessment

DLT events and assessments will be treated separately from the overall pharmacovigilance described in section 13.0.

Patients will be screened for DLT events once a day (this can be at any point during a 24-hour period) from the start of the intervention until five hours after the completion of the last dose or hospital discharge, whichever occurs first. DLT event screening will also occur in control patients from days 1-11 to compare the event rates with the intervention arm. Screening for DLT events will occur by reviewing routinely collected clinical laboratory tests and clinical examination in the first place. Blood tests include electrolytes, glucose, serum creatinine, liver enzymes (serum ALT, AST, ALP, y-glutamyl transpeptidase) and total serum bilirubin, serum triglycerides, blood count (leukocytes, platelets, red blood cells, neutrophils, lymphocytes, monocytes, eosinophils, basophils, and nucleated red blood cell count) and coagulation measures (prothrombin time, PTR/INR, activated partial thromboplastin time), and acid-base metabolism. If these measures are not available routinely, they will be mandated by the research team. Similarly, daily vital sign measurements (heart rate, blood pressure, body temperature, fluid balance and respiratory rate) will be taken by the research team, if not performed as part of routine care. These results will be noted in the Case Report Form (CRF).

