The DLT assessment will be performed by a three-member panel comprising of two independent assessors (Consultant Gastroenterologists) and the Chief Investigator (CI) after the completion of each dosing phase. The panel will be blinded to study arm allocation (intervention or control). In the event that the CI does become unblinded, the delegated sub investigator will replace the CI on the adjudication panel.

Potential DLT events are defined as either a pre-specified AE or serious adverse event (SAE) attributable to Omegaven, as listed in **Table 1.**^{28 29} The pre-defined AEs and SAEs have been taken from the "undesirable effects" section in the SmPC for Omegaven, considering effects deemed unacceptable. Thrombophlebitis has also been added to this list and the range for hyper-triglyceridaemia adjusted based on previously published data.³⁰ To make provision to address any undesirable effects not listed in the SmPC, "Other" has been added to Table 1 as well. These are medical events of concern to the consultant in charge of direct patient care

with potential to be related to Omegaven. Patients will be monitored by senior clinicians at least twice a day as part of standard care. On occurrence of a medical event of concern, the research team will be notified and will assess the event against the US National Cancer Institute guidance document of Common Terminology Criteria for Adverse Events (CTCAE) version 5.0 ³¹, and will record a potential DLT event, if the event is determined as Grade 3 or higher (Figure 1). Following the identification of an event listed in **Table 1**, relatedness to Omegaven will be assessed to determine if the event will be classified as a DLT event.³² This will be based on a tiered assessment (WHO-UMC causality categories, **Table 2**).³³ If the predefined AEs and SAEs in **Table 1** are deemed as definitely or probably/likely related to the intervention, they will be counted towards the DLT assessment.

[figure not shown]

Figure 1 Flow diagram for "Other" DLT identification: The figure describes the steps of identification of an "Other" DLT for the HIPPO trial.

CTCAE: Common Terminology Criteria for Adverse Events

Table 1: DLTs defined for the HIPPO trial

DLT events	Description	Initial identification	Criteria	Time scale for consideration	Action (related to trial)

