The BOIN intervention algorithm for the HIPPO trial is shown in **Figure 2**. ³⁵ ³⁶ Cut-offs for the escalation and de-escalation boundaries for the DLT rate were obtained using software available at www.trialdesign.org, using the following input parameters:

- three doses
- target toxicity rate for the maximum tolerable dose 0.30 (30%)
- patients recruited in cohorts of nine,
- maximum sample size is 27
- 0.80 probability cut-off for overdose control

Upon the completion of each dosing phase (defined as at least five hours after the last patient in the phase has finished the last dose of Omegaven), the DLT rate will be computed as follows, and compared with the cut-offs shown in **Figure 2** before treating the next cohort of patients:

DLT rate = Number of patients who experienced DLT at current dose

Total number of evaluable patients treated on current dose

Following the DLT assessment and based on the DLT rate, the next nine intervention patients will either:

- 1) receive the next highest dose if the observed DLT rate on the current dose is ≤0.236
- 2) remain on the same dose if the observed DLT rate is >0.236 and <0.359
- 3) de-escalate to the next lowest dose if the observed DLT rate is >0.359

If de-escalation is indicated on the lowest dose, the next cohort of patients will continue at the lowest dose. If the probability of the observed DLT rate being greater than the target DLT is >0.80 and if at least three patients are treated at the current dose, the dose is too toxic. Therefore, this dose and any higher doses will be eliminated. If the lowest dose is too toxic, the trial must be terminated.

After the panel meeting that will be held following completion of each dosing phase, a report will be drafted and agreed on by all panel members in a timely manner. The report which will include the recommended dosing plan for the next cohort of patients will be signed off by the trial statistician within two weeks of receipt. Once these approvals are in place, the next cohort of patients will be recruited. These approvals will be filed in the ISF and TMF. Each DLT assessment report will also be reported to the Data Monitoring and Ethics Committee (DMEC) for information only.

[figure not shown]

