Figure 2 Intervention algorithm: The figure describes the BOIN dose-escalation and de-escalation plan for the HIPPO trial. At each stage, the DLT events rate will be used to assess whether the dose will be escalated, retained, or de-escalated. The stopping rule at each dosing phase is defined as "Is the maximum sample size reached?". After the stopping rule is met, the maximum tolerable dose (MTD) will be calculated, which is the primary outcome of the trial. Note: If the lowest dose is eliminated due to

DLT = Dose-limiting toxicity, from a list of pre-specified adverse or serious adverse events attributable to Omegaven (Table 1).

toxicity the trial is stopped, and no maximum tolerable dose can be obtained.

BOIN design implementation

The following steps detail the BOIN design implementation plan for the HIPPO trial.

- 1. Treat patients in the first cohort (nine patients) at the lowest dose (0.2 g/kg/d) of Omegaven
- 2. Perform DLT assessment as described above
- 3. Calculate DLT rate

DLT rate = Number of patients who experienced DLT at current dose

Total number of evaluable patients treated on current dose

- 4. Assign a dose to the next cohort of patients:
 - Conduct dose-escalation/de-escalation according to the rule displayed in **Table 3**. Notes for using Table 3:
 - a. "Eliminate" means eliminate the current and higher doses from the trial to prevent treating any future patients at these doses because they are overly toxic.
 - b. When a dose is eliminated, the next cohort is automatically de-escalated to the dose on the next lower level. When the lowest dose is eliminated, the trial is stopped for safety. In this case, no dose should be selected as the maximum tolerable dose.
 - c. If none of the actions (i.e., escalation, de-escalation or elimination) is triggered, the new cohort of patients are treated at the current dose.
 - d. If the current dose is the lowest dose and the rule indicates dose de-escalation, the new cohort of patients should be treated at the lowest dose unless the number of DLT events reaches the elimination boundary, at which point the trial is stopped for safety.
 - e. Number of DLT events in **Table 3** is the number of patients with at least one DLT events, therefore a patient will only be counted once for DLT events assessment, independent of the number of DLT events the patient experiences.

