- Repeat step four until the maximum sample size of 27 patients receiving the intervention is reached, or stop the trial early if the number of patients experiencing DLT events at the lowest dose level reaches the elimination boundaries listed in **Table** In the latter case, no dose should be selected as the maximum tolerable dose.

Table 3 Escalation/De-escalation Rule for the HIPPO trial: The table details the rules when to escalate, retain, de-escalate or eliminate a treatment dose in the HIPPO trial, based on number of patients with DLT events (Table 1), considering the total number of patients treated with that dose. For HIPPO, cohorts of nine (highlighted columns) are treated. The last row represents the number of patients with DLT events at which the dose is deemed too toxic, and that dose and any higher dose will be eliminated.

Escalation/De-escalation Rule

Number of evaluable patients treated	3	4	5	6	7	8	9	10	11	12	13	14	15	16	17	18	19	20	21	22	23	24	25	26	27
Escalate if # of DLT <=	0	0	1	1	1	1	2	2	2	2	3	3	3	3	4	4	4	4	4	5	5	5	5	6	6
Stay if # of DLT =	1	1	NA	2	2	2	3	3	3	3-4	4	4-5	4-5	4-5	5-6	5-6	5-6	5-7	5-7	6-7	6-8	6-8	6-8	7-9	7-9
De-escalate if # of DLT >=	2	2	2	3	3	3	4	4	4	5	5	6	6	6	7	7	7	8	8	8	9	9	9	10	10
Eliminate if # of DLT >=	2	2	3	3	3	4	4	5	5	5	6	6	6	7	7	7	8	8	8	9	9	9	10	10	10

DLT = dose-limiting toxicity

of DLT is the number of patients with at least 1 DLT

NA = not applicable (no rule available for staying on same dose in this scenario – plan is to either escalate or deescalate)

Further notes:

Dose-escalation will occur if applicable, to the second (0.4 g/kg/d Omegaven) and third dose (0.6 g/kg/d Omegaven). If no dose-escalation can be performed, another nine participants will either be treated at the same or the lower dose, guided by the dose-escalation plan, leading to 27 patients receiving the intervention, and an additional 9 patients in the control group, to reach the maximum sample size of 36 patients.

The trial will stop if the stopping rule is met (once the maximum sample size for the trial has been reached), irrespective of which doses have been tested; or if the elimination rule is met on the lowest dose (the lowest dose is found to be too toxic) (lowest row in **Table 3**). The maximum sample size for this trial is 36 patients (27 patients receiving the intervention in cohorts of 9 patients, plus 9 control patients).

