For example, after treating nine patients in one phase of the dose-escalation trial the DLT events rates in **Figure 2** translate to the following, as described in **Table 3**:

- If ≤2 patients experience DLT events, the dose can increase to the next higher dose
- If 3 patients experience DLT events, another nine patients will be treated with the same dose
- If ≥4 patients experience DLT events, the current dose and higher doses are eliminated, and the dose has to be de-escalated to the next lower dose.

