15.0 Statistical and data analysis

15.1 Sample size calculation

A total of 36 participants will be recruited (randomised 1:3 control:intervention). The number of participants treated on each dose of Omegaven will be determined by the escalation / deescalation rule specified in the BOIN design shown in Figure 2 and Table 1, which aims to exclude a toxicity rate of ≥ 30%. The minimum number of participants to be treated on a single dose is nine and the maximum is 27. Assuming mortality of approximately 20-30% in critically ill patients, we will replace up to a maximum of three patients in each study phase in case of patient death, or withdrawal. There is no formal assessment of sample size required for a phase I dose escalation trial, however 36 participants (nine control and 27 intervention) will be sufficient to provide pilot data on the exploratory outcomes. A published study with eight patient samples per group enabled examination of the p38 inhibitor and identification of a doubling in proliferation and cytotoxicity as measured by granzyme and perforin expression using nine patients per group would provide almost 80% power to detect a mean difference of 12 in %CD107a CD8+ EMRA T cells (assuming SD=6 and α=0.05) (unpublished data, [name])¹⁵. Early phase trials often use less conservative type I error rates as they can be considered screening studies to inform a future definitive trial; with this sample size the trial would have 87.4% power for α =0.1 and 94.4% for α =0.2 using the parameters given above.

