15.2 Planned recruitment rate

The estimated planned recruitment rate is two to three patients per month. Since the inclusion criteria is all adult patients predicted stay of 72 hours in critical care, we are aiming to finish the study over a 12–15-month recruitment period. The CI has a track record of leading research studies like ASICS ⁴⁴ and PROSPER. The study coordinator is responsible for driving recruitment and support and encourage the delivery team to meet the recruitment target.

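### No numeric rule pauses new Omegaven starts within a cohort once the end-of-phase elimination count has been reached

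*Protocol*

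**What the plan says.** Protocol section 2.6 sets a daily check: "Patients will be screened for DLT events once a day". Adjudication comes later. The panel is two independent assessors and "the Chief Investigator (CI) after the completion of each dosing phase". The DLT rate is then computed: "Upon the completion of each dosing phase (defined as at least five hours after the last patient in the phase" has finished its last dose. Table 3 is applied to that rate to choose the dose for the next cohort of nine. The worked example for nine patients reads: "If ≥4 patients experience DLT events, the current dose and higher doses are eliminated". Section 15.12 confirms that there is no interim analysis, only a safety assessment before each escalation.

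For the lowest dose, the implementation steps say to "stop the trial early if the number of patients experiencing DLT events at the lowest dose level reaches the elimination boundaries", and note d says the lowest dose continues "unless the number of DLT events reaches the elimination boundary, at which point the trial is stopped for safety". Neither states when within a cohort the count is looked at.

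Two other provisions matter here. Section 15.1 says "we will replace up to a maximum of three patients in each study phase in case of patient death, or withdrawal", and section 15.2 says "The estimated planned recruitment rate is two to three patients per month".

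**The concern.** Note a under step 4 of the BOIN implementation gives the purpose of elimination: no further patients should be treated at an overly toxic dose. With slow accrual and a 10-day course, most DLTs in early patients will be visible before the later patients of the same cohort start. If four of the first six Omegaven patients have related DLTs, the protocol as written still allows patients seven to nine to start that dose, although Table 3 will remove it if the cohort ends with nine evaluable.

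The other brakes carry no count that requires a pause. They are contact with the CI and stopping the infusion for hypertriglyceridaemia (Table 1), reducing or stopping an infusion for Omegaven-related events (11.12), clinician withdrawal (9.0), SAE reporting and review (13.7, 13.8), urgent safety measures (13.10), and TSC and DMEC oversight (24.2, 24.3). DLT reports go to the DMEC for information only. At stake is exposure of critically ill patients, some with conditions the SmPC lists as contraindications, to a dose that is about to be dropped.

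**Working it through.** **Inputs (sections 2.6, 8.3, 15.1 and 15.2).** Target rate 0.30; overdose cut-off 0.80; cohorts of nine; maximum 27 on Omegaven; 1:3 control:Omegaven allocation; 2–3 patients a month; up to three replacements per phase. No DLT rate is given, so all true rates below are assumptions.

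**The plan's own figures.** With alternatives of 0.6 and 1.4 times the target (assumed, as the protocol does not state them), the BOIN cut-offs are 0.2365 and 0.3585, matching 0.236 and 0.359. Taking elimination as the smallest y with P(rate > 0.30 | y, n) > 0.80 under a Beta(1,1) prior (also assumed), the elimination row agrees at every n from 3 to 27, as do the escalation and de-escalation rows. For example, 3/9 gives 0.650 and 4/9 gives 0.850; 7/18 gives 0.818; 10/27 gives 0.809.

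**Is there time to act?** 2–3 a month × 0.75 = 1.5–2.25 Omegaven starts a month. Nine starts take 9/2.25 = 4 to 9/1.5 = 6 months, against a 10-day course.

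**First cohort, nine evaluable, each DLT known before the next start.** P(fourth DLT before patient nine) = P(Bin(8, p) ≥ 4). Mean later starts = Σ over m = 4…9 of (9 − m)·C(m−1, 3)·p⁴·(1−p)^(m−4).

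| True rate | Eliminated at nine, P(Bin(9, p) ≥ 4) | Fourth DLT before patient nine | Mean later starts |
|---|---|---|---|
| 10% | 0.008 | 0.005 | 0.01 |
| 20% | 0.086 | 0.056 | 0.11 |
| 30% | 0.270 | 0.194 | 0.43 |
| 40% | 0.517 | 0.406 | 0.99 |
| 50% | 0.746 | 0.637 | 1.73 |

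At 30% the mean is 5(0.0081) + 4(0.0227) + 3(0.0397) + 2(0.0556) + 1(0.0681) = 0.43.

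**Overlapping courses.** Simulating random arrivals at 1.5–2.25 starts a month, with the DLT somewhere in the 10 days or at their end, the chance of at least one later start is 0.04–0.05, 0.15–0.18, 0.32–0.38 and 0.53–0.60 at 20%, 30%, 40% and 50%.

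**Whole trial.** Exact enumeration of three cohorts of nine under Table 3, at rates of 5/10/20%, 10/20/30%, 10/30/50% and 30/45/60% across the doses, gives at least one later start in 6%, 21%, 52% and 64% of trials (mean 0.12, 0.44, 1.30 and 1.60 patients). This assumes exactly nine evaluable per cohort and events known before the next start.

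**Effect of the relatedness judgement.** Suppose 30% of Omegaven patients have a potential DLT. If half are judged related, the counted rate is 0.30 × 0.5 = 15% and mean later starts are 0.04. If 80% are, the rate is 24% and the mean is 0.21. A first pause, called when four patients have unadjudicated potential DLTs, is confirmed with probability 0.5⁴ = 0.06 or 0.8⁴ = 0.41.

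**Effect of replacement.** If replaced patients stay evaluable, n may end at 10–12, where Table 3 needs five DLTs to eliminate; 4/10 and 4/11 mean de-escalate and 4/12 means stay. At a 30% rate, the share of cohorts with a fourth DLT by patient eight that end at exactly four is P(Bin(8, 0.3) = 4)·0.7^(n−8) / P(Bin(8, 0.3) ≥ 4) = 0.1361·0.7^(n−8)/0.1941. That is 34%, 24% and 17% for n = 10, 11 and 12.

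**The case against.** The strongest reply is that nothing here is wrong. The protocol declares a cohort-wise BOIN design, and sections 2.6 and 15.12 agree that events are adjudicated after each phase and then used to choose the next dose. A within-cohort pause is an addition. That stands as a description of the design, and it is why this is an improvement rather than an error.

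A reader might infer that the fourth DLT in a cohort already fixes elimination. The documents do not support that. Mid-phase events are only potential DLTs until the panel judges them certain or probable, and the final evaluable number is not known while replacements are possible.

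A reader might also take the lowest-dose wording, with the rule's minimum of three patients and the Table 3 columns for n = 3–8, as a stop checked after every patient. That would be a different design. It would end the trial in the first 0.2 g/kg/d cohort with probability 6.2%, 23.5% and 46.4% at true rates of 10%, 20% and 30%, against 0.8%, 8.6% and 27.0% at nine patients. It is not workable as written: no adjudicated count exists until the phase ends, the stop sits inside the step that assigns the next cohort's dose, and Table 3 is used in cohorts of nine. One clarifying sentence is enough.

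Two further points stand. Clinical discretion may stop recruitment in practice, and the DMEC's early-termination process is left to a remit not shown, so a count-based rule there cannot be excluded. A pause also has real costs, set out with the fix.

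**Conclusion.** The Table 3 boundaries are correct and the end-of-phase design is internally consistent. What the protocol lacks, at any dose, is a numeric rule to pause new Omegaven starts when the end-of-phase elimination count is reached within a cohort, so patients may start a dose that is about to be eliminated.

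Per first cohort the exposure is about 0.1 patient at a true rate of 20%, 0.4 at 30%, 1.0 at 40% and 1.7 at 50%. It is less once relatedness is judged, and generally less when courses overlap. These sizes rest on assumed DLT rates, nine evaluable patients and prompt knowledge of events. The benefit is small at 20% or less and largest when a dose is truly toxic. This is a modest safety improvement.

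**What to change.** In section 2.6, under the dose-escalation plan, add the following.

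- **Trigger.** When Omegaven patients at the current dose with confirmed plus unadjudicated potential DLTs reach the Table 3 elimination count for the planned end-of-phase number (4 of 9, 7 of 18, 10 of 27), pause new randomisations in that phase. The existing panel adjudicates early, with control cases included to protect its blinding.
- **Action.** Eliminate the dose, or stop the trial at 0.2 g/kg/d, only if the adjudicated count meets the boundary for the largest evaluable number the phase can still reach, given replacements made or still allowed (five if n may end at 10–12). Alternatively, first fix that replaced patients do not add to the evaluable number, and how a DLT in a replaced patient counts, so that 4 of 9 is final. Otherwise resume, with any further potential DLT reopening the review.
- **Lowest dose.** State in the implementation steps that the lowest-dose stop uses this same trigger and that the n = 3–8 columns are not applied continuously.

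Because the elimination row never falls as n rises, a count that meets the boundary for the largest reachable n would eliminate at any smaller n too, so end-of-phase elimination decisions do not change. If unused slots are not refilled, the MTD choice is also unchanged. An eliminated dose has an observed rate of at least 10/27 = 0.370, above the 0.359 limit in section 15.4, and so does any lower dose pooled with it. In simulation, refilling the slots moved selection by about 1 percentage point at most.

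The cost is wording and occasional early panel meetings, with no extra patients. Some pauses will end in resumption: at a 30% potential-DLT rate, 19% of first cohorts would pause before patient nine. Eligible patients may be lost meanwhile, because treatment must start within 48 hours of critical care admission. There is some risk to the panel's blinding, since a pause itself signals the Omegaven count. An eliminated dose would yield slightly fewer data and an upward-biased observed rate, and controls may number fewer than nine.
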